## **4.2 METHOD OF TREATMENT ASSIGNMENT AND BLINDING**

After written informed consent and assent have been obtained, all patients will receive a screening number, which will be assigned by an interactive voice/Web-based response system (IxRS). Following completion of the screening period and after all patient eligibility requirements are confirmed, patients will be assigned a patient number (a different number from the screening number) on Day 1 and will undergo randomization in a 1:1 ratio to receive either high-frequency dose of etrolizumab once every 4 weeks or low-frequency dose of etrolizumab once every 8 weeks.

Randomization will be stratified by weight (<40 kg,  $\geq$ 40 kg). A permuted blocks randomization method will be used to obtain an approximately 1:1 ratio between the two treatment arms within each stratum.

This is an open-label study, and no blinding of site, patient, or Sponsor will be implemented. The primary objective is estimation of PK and PD parameters which can be performed objectively without blinding of the dose frequency received (low vs high).

## **4.3 STUDY TREATMENT AND OTHER TREATMENTS RELEVANT TO THE STUDY DESIGN**

The investigational medicinal product (IMP) for this study is etrolizumab. All patients will receive etrolizumab one subcutaneous injection of 0.01 mL per kg of patient weight (1.5 mg/kg) Q4W or injection of 0.02 mL per kg of patient weight (3 mg/kg) Q8W.

### **4.3.1 Study Treatment Formulation, Packaging, and Handling**

#### **4.3.1.1 Etrolizumab**

F. Hoffmann-La Roche Ltd manufactures etrolizumab drug product. Etrolizumab drug product is a colorless to slightly yellow solution. The drug product is a sterile and preservative-free liquid intended for SC administration.

The drug product contains 150 mg/mL of etrolizumab in 200 mM L-arginine succinate, 20 mM L-histidine, and 0.04% (w/v) polysorbate 20, pH 5.8. Etrolizumab drug product will be provided in single-use, 3-cc glass vials that are stoppered with 13-mm fluororesin laminated stoppers and capped with aluminum seals with flip-off plastic caps.

For further details, see the etrolizumab (PRO145223, RO5490261) Investigator's Brochure.

Upon arrival of investigational products at the site, the pharmacist or designee should check them for damage and verify proper identity, quantity, integrity of seals, and temperature conditions, and report any deviations or product complaints to the monitor upon discovery.

The study drug must be stored according to the details on the product label. The drug label indicates the storage temperature.

Under no circumstances is the investigator to allow study medication to be used other than as directed by the protocol.

Details about the packaging and labeling of the study drug will be provided in the protocol-supporting documents that include but are not limited to the study manual and laboratory manual.

For further details, see the current Investigator's Brochure.

#### **4.3.2 Study Treatment Dosage, Administration, and Compliance**

##### **4.3.2.1 Etrolizumab**

The treatment regimens are summarized in Section [3.1](#).

Etrolizumab will be administered at the site during the randomized treatment phase. During the OLE phase, etrolizumab may be administered at the site.

Patients will receive treatment with etrolizumab 1.5 mg per kg patient weight SC Q4W weeks or 3 mg per kg patient weight SC Q8W. Injections will be administered to the abdomen. If the abdomen is not available for injection, the patient may receive a SC dose in the thigh. Each patient will receive one SC injection of 0.01 mL per kg patient weight or injection of 0.02 mL per kg of patient weight at each treatment visit based on the treatment regimen (the low or high frequency arm).

Etrolizumab vials are stable at 2°C–8°C (36°F–46°F). Etrolizumab vials should not be frozen or shaken and should be protected from direct sunlight.

Any overdose or incorrect administration of etrolizumab should be noted on the Study Drug Administration electronic Case Report Form (eCRF). Adverse events associated with an overdose or incorrect administration of any of the study treatments should be recorded on the Adverse Event eCRF.

Guidelines for etrolizumab treatment interruption or discontinuation for patients who experience adverse events are provided in Section [5.1](#).

Patients will be monitored for acute hypersensitivity reactions for at least 1 hour after the end of the injection. Epinephrine and parenteral diphenhydramine must be readily available for immediate use if required to treat a hypersensitivity reaction; site personnel must be able to detect and treat such reactions.

Guidelines for etrolizumab administration will be provided in supporting documents.

#### **4.3.3 Investigational Medicinal Product Accountability**

All IMPs required for completion of this study (etrolizumab) will be provided by the Sponsor where required by local health authority regulations. The study site will acknowledge receipt of IMPs using the IxRS to confirm the shipment condition and content. Any damaged shipments will be replaced.

IMPs will either be disposed of at the study site according to the study site's institutional standard operating procedure or will be returned to the Sponsor with the appropriate documentation. The site's method of IMP destruction must be agreed to by the Sponsor. The site must obtain written authorization from the Sponsor before any IMP is destroyed, and IMP destruction must be documented on the appropriate form.

Accurate records of all IMPs received at, dispensed from, returned to, and disposed of by the study site should be recorded on the Drug Inventory Log.

#### **4.3.4 Continued Access to Etrolizumab**

The Sponsor will offer continued access to Roche IMP etrolizumab free of charge to eligible patients in accordance with the Roche Global Policy on Continued Access to Investigational Medicinal Product, as outlined below.

A patient will be eligible to receive Roche IMP etrolizumab after completing the study if all of the following conditions are met:

- The patient has a life-threatening or severe medical condition and requires continued Roche IMP treatment for his or her well-being
- There are no appropriate alternative treatments available to the patient
- The patient and his or her doctor comply with and satisfy any legal or regulatory requirements that apply to them

A patient will not be eligible to receive Roche IMP etrolizumab after completing the study if any of the following conditions are met:

- The Roche IMP is commercially marketed in the patient's country and is reasonably accessible to the patient (e.g., is covered by the patient's insurance or wouldn't otherwise create a financial hardship for the patient)
- The Sponsor has discontinued development of the IMP or data suggest that the IMP is not effective for etrolizumab
- The Sponsor has reasonable safety concerns regarding the IMP as treatment for etrolizumab
- Provision of the Roche IMP is not permitted under the laws and regulations of the patient's country

The Roche Global Policy on Continued Access to Investigational Medicinal Product is available at the following Web site:

[http://www.roche.com/policy\\_continued\\_access\\_to\\_investigational\\_medicines.pdf](http://www.roche.com/policy_continued_access_to_investigational_medicines.pdf)

## **4.4 CONCOMITANT THERAPY**

Concomitant therapy consists of any medication (e.g., prescription drugs, over-the-counter drugs, vaccines, topical medications, herbal or homeopathic remedies, nutritional supplements) used by a patient in addition to protocol-mandated treatment from 8 weeks prior to initiation of study drug to the study completion/discontinuation visit. All such medications should be reported to the investigator and recorded on the Concomitant Medications eCRF. The doses of these therapies do not have to be stable at the time of screening and during the study period.

### **4.4.1 Permitted Therapy**

Patients are permitted to use the following therapies during the study:

- Oral contraceptives
- Hormone-replacement therapy (e.g., growth hormone therapy)
- Steroids (IV, oral, or topical)
- 5-ASA (oral or topical)
- Immunosuppressants (i.e., AZA, 6-MP, or MTX)

Premedication with antihistamines, antipyretics, and/or analgesics may be administered at the discretion of the investigator.

In general, investigators should manage a patient's care with supportive therapies as clinically indicated, per local standard practice.

#### ***4.4.1.1 Coronavirus Disease 2019 Vaccines***

*Treatment decisions regarding the use of coronavirus disease 2019 (COVID-19) vaccines for patients eligible to receive them should be based on the physician's best clinical judgment. Based on a review of the underlying disease biology, patient population, the mechanism of action of etrolizumab, and the information available to date on COVID-19 vaccines, it is unlikely that etrolizumab will have an impact on the efficacy of currently approved COVID-19 vaccines (mRNA vaccines, inactivated vaccines, and replication deficient adenovirus vaccines) or that these currently approved vaccines will impact the safety or efficacy of etrolizumab.*

*COVID-19 vaccines should be documented in the CRF as concomitant medication. For more detailed questions or questions about specific types of COVID-19 vaccines, please contact the Medical Monitor.*

#### **4.4.2        Cautionary Therapy**

##### **4.4.2.1      Herbal Therapies**

Concomitant use of herbal therapies is not recommended because their pharmacokinetics, safety profiles, and potential drug-drug interactions are generally unknown. However, herbal therapies not intended for the treatment of UC or CD may be used during the study at the discretion of the investigator.

##### **4.4.2.2      Rescue Therapies**

The worsening of UC or CD may result in the use of rescue medications, based on the discretion of the Principal investigator.

At any time during the study, patients who have worsening of their UC or CD will be permitted to receive additional therapy with steroids (IV, oral, or topical). Addition of or increases in doses of 5-ASA (oral or topical) and/or immunosuppressants (i.e., AZA, 6-MP, or MTX) will also be allowed if clinically indicated by the Principal Investigator.

Rescue therapy with anti-TNF agents or their corresponding biosimilars, cyclosporine, tacrolimus, sirolimus, MMF, anti-adhesion molecules, natalizumab, vedolizumab, ustekinumab, efalizumab, rituximab, other lymphocyte depleting agents (except AZA and 6-MP), or other biological or investigational therapeutics will not be allowed in conjunction with etrolizumab because of the level of immunosuppression anticipated with the use of these agents. Patients who receive such therapies are not to receive further study treatment or enter the open-label treatment phase, and will be required to enter safety follow-up period. All patients will be offered participation in the 104-week PML monitoring phase (*includes 12-week safety follow-up period after completion or early discontinuation from OLE*).

#### **4.4.3        Prohibited Therapy**

Use of the following concomitant therapies is prohibited during the 24-week randomized treatment phase as described below:

- Any investigational treatment or experimental therapy including investigational vaccines and biologic agents
- Use of lymphocyte-depleting agents (e.g., alemtuzumab or visilizumab), except for AZA and 6-MP
- Use of cyclosporine, tacrolimus, sirolimus, or MMF
- Use of natalizumab, vedolizumab, ustekinumab, or rituximab
- Use of TNF inhibitors, including biosimilars
- Use of anakinra or abatacept and/or other biological therapeutics
- Use of *other* anti-adhesion molecules
- Use of other biologic agents

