### **3. STUDY DESIGN**

#### **3.1 DESCRIPTION OF THE STUDY**

This pediatric PK/PD study consists of multiple phases. The randomized treatment phase is an open-label, randomized phase in which etrolizumab is administered to patients on the basis of body weight (mg/kg); randomization will be stratified by weight (<40 kg, ≥40 kg). Patients will be randomized in a 1:1 ratio to receive either high-frequency etrolizumab once every 4 weeks (Q4W) or low-frequency etrolizumab once every 8 weeks (Q8W). The high-frequency dose of 1.5 mg/kg etrolizumab will be administered Q4W (Weeks 0, 4, 8, and 12). The low-frequency dose of 3.0 mg/kg etrolizumab will be administered Q8W (Weeks 0 and 8).

After the 24-week randomized treatment phase (which includes a 16-week treatment period and an 8-week safety follow-up period), patients will then have the option to participate in the 312-week OLE phase (treatment with etrolizumab 1.5 mg/kg will be administered Q4W). All patients who participate in the 24-week randomized treatment phase and the 312-week OLE phase *will enter the 12-week safety follow-up period (see Appendix 1d; no etrolizumab treatment) and will complete the safety surveillance PML-monitoring phase (see Appendix 1e; no etrolizumab treatment for a total of 104 weeks)*. All patients who choose not to enter the OLE phase after the 24-week randomized treatment phase will enter the 104-week PML monitoring phase.

Patients can enter the OLE phase after completion of the 24-week randomized treatment phase. If the last visit of the randomized treatment phase and Day 1 of the OLE phase occur on the same day, the assessments from the randomized treatment phase should be completed. The assessments from the randomized treatment phase can apply to the OLE assessments (i.e., the same assessments should not be repeated for the OLE).

The 104-week PML monitoring phase will consist of telephone calls approximately every 6 months (see [Appendix 7](#)) with administration of the PML Subjective Checklist. If there are any signs or symptoms suggestive of PML identified on this subjective checklist during the telephone call, the patient will be asked to come into the clinic for a neurologic examination. The PML Algorithm (see [Appendix 8](#)) will be followed for any suspected

case of PML, and any confirmed case of PML will be reported as a serious adverse event (see Section 5.4.2).

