### **4.6 TREATMENT, PATIENT, STUDY, AND SITE DISCONTINUATION**

#### **4.6.1 Study Treatment Discontinuation**

Patients must permanently discontinue study treatment if they experience any of the following:

- Any medical condition that the investigator or Sponsor determines may jeopardize the patient's safety if he or she continues to receive study treatment
- Investigator or Sponsor determines it is in the best interest of the patient
- Pregnancy
- Anaphylaxis or other severe hypersensitivity reaction
- Develop colonic mucosal dysplasia
- Malignancy (with the exception of local and resected basal or squamous cell carcinoma of the skin) or cervical Pap test with AIS, HSIL, or CIN of Grade >1

- Specific serious infection (see Section 5.1.1.1 for details on serious infection):
  - Any patient who experiences a specific de novo or reactivated serious viral infection, such as HBV, HCV, HIV, should discontinue study medication.
  - Any patient who develops life-threatening infections during the study should discontinue study medication.

The primary reason for study treatment discontinuation should be documented on the appropriate eCRF.

Patients will return to the clinic for an early withdrawal from treatment or treatment discontinuation visit after the last dose of study drug (see [Appendix 1](#) for additional details).

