### **Screening, Patient Selection, and PML Education**

No known interventions can reliably prevent or treat PML if it occurs; therefore, it is important to exclude patients with a perceived higher baseline risk for PML, such as patients who have received natalizumab, efalizumab, rituximab, B or T cell depleting agents (e.g., alemtuzumab or visilizumab), with the exception of AZA and 6-MP, cyclosporine, tacrolimus, sirolimus, or MMF. Patients with a history of PML or neurological symptoms where suspected PML has not been ruled out are not eligible for this study (see Section 4.1.2).

A blood sample to test for antibodies to JCV will be taken and stored for possible later assessment of how widespread the JCV infection is in the study population. Sample testing for the presence of JCV antibodies is not helpful in predicting risk for PML or for evaluating neurologic symptoms. The sample may be tested if there is a strong belief that this information will be helpful in managing a patient's condition.

Study site personnel and patient participants should be educated regarding the signs and symptoms of PML. Patients and partners/caregivers should be issued with alert cards to remind them of these and to advise them to contact the investigator right away if they notice any new or worsening neurological abnormalities.

See [Appendix 1](#) for details of assessments regarding PML.

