### **5.1.1.7 Decreased Effectiveness of Immunizations**

#### **Background**

The effect of etrolizumab upon the efficacy of vaccinations is unknown. Whenever possible, necessary vaccinations should be performed at a minimum of 4 weeks prior to participating in a clinical trial with etrolizumab. Live attenuated vaccines should be administered at least 4 weeks prior to administration of etrolizumab and should not be administered for the duration of the clinical trial or for at least 2.5 months (approximately 5 half-lives) after final study drug administration (see Etrolizumab Investigators Brochure for reference).

These recommendations are in line with the most recent vedolizumab (ENTYVIO®) label according to which there are no data on the secondary transmission of infection by live vaccines in patients receiving ENTYVIO. In a placebo-controlled study of healthy volunteers, 61 subjects were given a single ENTYVIO 750 mg dose (2.5 times the recommended dose), and 62 subjects received placebo followed by intramuscular

vaccination with Hepatitis B surface antigen and oral cholera vaccine. After intramuscular vaccination with three doses of recombinant Hepatitis B surface antigen, those treated with ENTYVIO did not have lower rates of protective immunity to Hepatitis B virus. However, those exposed to ENTYVIO did have lower seroconversion rates and anti-cholera titers relative to placebo after receiving the two doses of a killed, oral cholera vaccine. The impact on other oral vaccines and on nasal vaccines in patients is unknown.

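### In the open-label extension, biologic, lymphocyte-depleting or investigational agents given for a non-IBD reason have no express bar, because the prohibited-therapy list is written for the 24-week randomized phase only

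*Combined protocol and SAP*

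**What the plan says.** - **Section 4.4.3** sets the period for the whole list: "Use of the following concomitant therapies is prohibited during the 24-week randomized treatment phase as described below". The items cover investigational treatment, lymphocyte-depleting agents, cyclosporine, tacrolimus, sirolimus, MMF, named and other biologics, and anti-adhesion molecules. None is tied to a reason for use.
- **Section 3.1** describes what follows: "patients will then have the option to participate in the 312-week OLE phase", with dosing every 4 weeks. It also makes rescue therapy available in every phase, and names the OLE.
- **Section 4.4.2.2** is triggered by worsening of UC or CD. Its bar begins "Rescue therapy with anti-TNF agents or their corresponding biosimilars, cyclosporine, tacrolimus, sirolimus, MMF", goes on to other biological or investigational agents, and says these "will not be allowed in conjunction with etrolizumab because of the level of immunosuppression anticipated with the use of these agents". The consequence is: "Patients who receive such therapies are not to receive further study treatment or enter the open-label treatment phase".
- **Section 4.4.1** lists therapies permitted during the study. For immunosuppressants it gives AZA, 6-MP and MTX after 'i.e.'.
- **Section 4.6.1** has no trigger for receiving a listed agent or joining another drug study. Its general triggers include "Investigator or Sponsor determines it is in the best interest of the patient".
- **Section 5.1.1.7** shows a rule written for the full period: live vaccines "should not be administered for the duration of the clinical trial".

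**The concern.** The reason Section 4.4.2.2 gives for keeping these agents away from etrolizumab is the combined immunosuppression. That does not depend on why the second drug was prescribed. Yet the rule that ignores indication ends at Week 24, while the rule that reaches the OLE is framed around IBD flares.

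A child on OLE dosing could start a biologic for a newly diagnosed non-IBD condition, or join another drug study. A site that reads Section 4.4.2.2 as a rescue rule would find no text telling it to stop etrolizumab. Concomitant medication is recorded at OLE visits (Appendix 1c), so the case would be seen and could be described, but not prevented. Infections and malignancies are OLE safety endpoints (Table 2), so in a study of about 24 children even one such case would be hard to interpret.

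**Working it through.** The plan states no figure on this point, so the check is mainly a comparison of text.

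**Does any other rule close the gap in the OLE?**
1. *Section 4.4.2.2, read with Section 3.1.* It applies in the OLE and covers IBD rescue. In the stop sentence, 'such therapies' refers back to a sentence whose subject is rescue therapy. A broad reading (any receipt) is possible, and the stated reason supports it, but the grammar does not require it.
2. *Section 4.4.1.* It applies throughout the study. The 'i.e.' before AZA, 6-MP and MTX contrasts with the 'e.g.' used for hormone replacement in the same list. On the natural reading, cyclosporine, tacrolimus, sirolimus and MMF fall outside what is permitted. The list is not stated to be exclusive, and it does not address biologics or investigational drugs.
3. *Section 4.1.2.4.* The criterion on investigational treatment looks back from Day 1. It does not govern later use.
4. *Section 4.6.1.* Stopping is mandatory once the investigator or Sponsor judges it necessary, but the judgment has to be made first.
5. *Section 4.6.2.* Withdrawal for non-compliance needs a protocol requirement to have been breached, and here that requirement is what is missing.

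Result: what remains is biologic, lymphocyte-depleting or investigational agents used for a non-IBD reason during OLE dosing.

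**Calendar scope (a description of the schedule, not of risk).**
- Inputs: randomized phase 24 weeks (16 treatment + 8 follow-up) and OLE 312 weeks, both from Section 3.1.
- Child who completes the OLE: 24 + 312 = 336 weeks. Inside the Section 4.4.3 window: 24/336 = 7.1%. Outside: 312/336 = 92.9%.
- Child who stays 52 OLE weeks (an assumption): 24 + 52 = 76 weeks. Inside: 24/76 = 31.6%. Outside: 52/76 = 68.4%.
- Child who does not enter the OLE: no gap.
- Doses: 312/4 = 78 in a full OLE (79 if one is given at Week 312), against 4 or 2 in the randomized phase.

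**Number of children affected.** The documents give no rate of non-IBD use of these agents or of co-enrolment, so no estimate is possible.

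**The case against.** The strongest reply is that the realistic case is already covered. A child in this study who needs an anti-TNF or another biologic will most often need it for IBD, and that is barred in every phase. The immunosuppression rationale also invites sites to read the stop sentence broadly.

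Entry criteria shrink the remaining group. Section 4.1.2.5 excludes non-IBD conditions that could need more than 10 mg/day of prednisone equivalent, serious uncontrolled comorbidity, immune deficiency and demyelinating disease. Section 4.1.2.6 excludes organ transplant recipients. Section 4.6.1 compels stopping once it is judged necessary, and a Safety Monitoring Committee reviews safety throughout (Section 3.1.1). All of this stands, and it is why the point is minor. It does not supply the missing rule for new-onset or milder conditions, or for another drug study entered for a non-IBD reason.

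A reader might infer more than the documents support:
- *That the OLE has no restriction, or rests on Section 4.4.2.2 alone.* Sections 4.4.1 and 4.6.1 also apply there.
- *That 92.9% measures exposure to harm.* It is a share of calendar time.
- *That the PML section supports the whole list.* The statement that "it is important to exclude patients with a perceived higher baseline risk for PML" concerns risk at entry and does not name anti-TNF agents.
- *That the main results are at risk.* The primary PK/PD endpoints belong to the randomized phase (Table 1), where the full list applies.

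**Conclusion.** The gap is real but narrow. During OLE dosing, a biologic, lymphocyte-depleting or investigational agent used for a non-IBD reason, including through another drug study, has no express bar. Whether etrolizumab stops depends on how a site reads Section 4.4.2.2 or on individual judgment. The plan gives no reason for ending the any-indication rule at Week 24, and keeping the same agents out as rescue in all phases suggests that no relaxation was intended.

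This is a minor matter of safety scope. Few children are likely to be affected, on the assumption that the entry criteria remove many who would need such agents. The conclusion also assumes that 'such therapies' is read, as its grammar suggests, to mean rescue use; on the broader reading the gap would largely close. Sample size and the primary analysis are unaffected. The change is worth making because it is cheap and follows the plan's own stated reason.

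**What to change.** 1. In the Section 4.4.3 lead-in, state that the listed therapies are prohibited *for any indication*, during the randomized phase *and while etrolizumab is being given in the OLE phase*. Add that *therapies permitted in Section 4.4.1 remain permitted*. This protects growth hormone and COVID-19 vaccination under Section 4.4.1.1.
2. In the Section 4.4.2.2 stop sentence, insert *for any indication* after *therapies*.
3. For listed agents that Section 4.4.2.2 does not name, such as investigational vaccines, require consultation with the Medical Monitor before further dosing. This avoids new, undefined classes of biologic.

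The cost is amendment wording and a notice to sites. No new procedure or data item is needed, since concomitant medication is already collected at OLE visits. The second change also applies in the randomized phase, where these agents are already prohibited but Section 4.4.3 states no consequence. The downside is that a child who needs a listed agent for another condition, or who joins another drug study, must stop etrolizumab. Section 4.4.2.2 already accepts that trade for rescue use.
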